10.2 Analysis of Adverse Events

All adverse events will be coded using the most current version of the Medical Dictionary for Regulatory Activities (MedDRA). Adverse events will be summarized by primary MedDRA system organ class (SOC) and preferred term (PT). Subjects reporting more than one adverse event for a given PT will be counted only once for that term. Subjects reporting more than one adverse event within an SOC will be counted only once for the SOC total. Subjects reporting more than one adverse event will be counted only once in the overall adverse event total. For summaries by SOC and PT, the SOCs will be presented in alphabetical order and the PTs will be presented in alphabetical order within each SOC.

A treatment-emergent adverse event (TEAE) during the 26-week randomized treatment period is defined as:

- For subjects in OMT group who don't continue into Extension Period: any adverse event that begins or worsens in severity the day after randomization and within 30 days following the last visit.
- For subjects in OMT group and continue into Extension Period: any adverse event that begins or worsens in severity the day after randomization and within 30 days following the last visit during 26-week randomized treatment period or before the insertion of NJ/PEG-J (whichever is earlier).
- For LCIG treatment subjects who have all study tubes removed after their last study drug infusion, this includes all adverse events with onset on or after the date of the initial tube placement procedure and no more than 30 days following the last study tube removal, or no more than 30 days following the last LCIG infusion if there is no final device removal during the 26-week randomized treatment period.

A TEAE during Extension Period for OMT subjects will be defined as any adverse event that begins or worsens in severity after the NJ or PEG-J placement through 30 days after last LCIG infusion or final device removal (whichever is later).

A TEAE during the continuing LCIG treatment period will be defined as any adverse event in LCIG group that begins or worsens in severity after Week 26 visit through 30 days after last LCIG infusion or final device removal (whichever is later).

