5.1.3 Study Follow-Up

Follow-Up Visit (V9) (LCIG Subjects not Continuing on Commercial Product)

For subjects who are not continuing on LCIG (through commercial sources in countries where LCIG is approved and marketed), the PEG-J tube will be removed following the End of Study activities. A follow-up clinic visit will occur approximately one week later.

Commercial Transition Visits (LCIG Subjects Continuing on Commercial Product)

Study subjects in the LCIG group who complete participation in the study and for whom continuation of treatment with LCIG is judged appropriate by the Investigator will continue to receive LCIG until transition to commercial product is coordinated with the Sponsor's commercial affiliate.

Additional visits every 12 weeks from Week 26 will be schedule to monitor subject safety and allow for drug resupply until the subject transfer to commercial LCIG. Refer to [Table 3](#) of Section [5.3.1.1](#) for list of assessments. Drug resupply visits will also occur at 6 week intervals between the every 12 week safety assessments.

Upon transfer of subjects to commercial LCIG the monitoring of such therapy will be the responsibility of the subject's personal physician. All necessary support will be provided by the Sponsor's local representative. Follow-up care in these circumstances will be based on the judgment of the subject's personal physician and no formal collection of data will be conducted except for regular ADR-reporting in accordance with local instructions.

OMT Subjects

Study subjects in the OMT group who complete participation in the study are eligible to transition to commercial LCIG after end of study procedures if judged appropriate by their personal physician. This transition is not study related.

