5.2.1 Inclusion Criteria

Subjects must meet the following criteria in order to participate in this study.

1. Subject must have a diagnosis of idiopathic Parkinson's disease according to the United Kingdom Parkinson's Disease Society (UKPDS) Brain Bank Criteria. See [Appendix C](#) for UKPDS.
2. Subject demonstrates persistent motor fluctuations in spite of individually optimized treatment.
3. The subject's Parkinson's disease is levodopa-responsive.
4. Subject has had optimized treatment with available anti-PD medication and their motor symptoms are judged inadequately controlled on this optimized treatment.

Optimized treatment is defined as the maximum therapeutic effect obtained with pharmacological antiparkinsonian therapies when no further improvement is expected regardless of any additional manipulations of levodopa and/or other antiparkinsonian medication. This will be based on the Investigator's clinical judgment.

5. Subject and/or if applicable, their care-partner must be able to complete the Subject Dosing Diary and must be able to demonstrate the ability to operate, manipulate and care for the infusion pump and tubing.
6. Subject is eligible to transfer to commercial treatment of Duodopa after completing the study based on local country requirements.
7. Subject must have a minimum PDSS-2 total score of 18 at Baseline assessment.*
8. Subject must be able to understand the nature of the study and has had the opportunity to have any questions answered. Prior to the conduct of any study procedures (including any changes occurring in the subject's current therapeutic regimen), the subject, if judged by the PI to have decision-making capacity, must have voluntarily signed the Independent Ethics Committees/Institutional Review Board (IEC/IRB) approved Informed Consent. In the absence of subject's ability to provide the informed consent, the informed consent must have been signed by a person who has the legal right to act on behalf of the subject following national laws.
9. Male or female subjects at least 30 years of age.

If female, subject must be either postmenopausal defined as:

- Age > 55 years with no menses for 12 or more months without an alternative medical cause.
- Age ≤ 55 years with no menses for 12 or more months without an alternative medical cause AND an FSH level > 40 IU/L.

OR

- Permanently surgical sterile (bilateral oophorectomy, bilateral salpingectomy or hysterectomy).

OR

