8.1.4.2 Adverse Events

Adverse events will be coded using the most current version of the Medical Dictionary for Regulatory Activities (MedDRA). Adverse events will be summarized by primary MedDRA system organ class (SOC) and preferred term (PT). Subjects reporting more than one adverse event for a given MedDRA PT will be counted only once for that term. Subjects reporting more than one adverse event within an SOC will be counted only once for the SOC total. Subjects reporting more than one adverse event will be counted only once in the overall adverse event total.

Each adverse event will be categorized by severity (mild, moderate, severe) and by relationship to study treatment (reasonable possibility, or no reasonable possibility). Detailed search criteria for adverse events of special interest (AESIs) will be defined in a SAP prior to database lock.

A treatment-emergent adverse event (TEAE) is defined as:

- For OMT group: any adverse event that begins or worsens in severity the day after randomization and within 30 days following the last visit.
- For the LCIG group: any adverse event that begins or worsens in severity from the day of the initial device placement (NJ or PEG-J) through Week 26 Visit for those subjects continuing to LCIG commercial treatment, or through 30 days after final device removal for those subjects not continuing LCIG commercial treatment.

A summary of the number and percentage of subjects will be prepared for the following:

- TEAEs
- TE Serious AEs (including deaths)
- TEAEs leading to premature discontinuation of treatment
- TEAEs by maximum relationship to study drug
- TEAEs by maximum severity
- Treatment-emergent AESIs

Serious adverse events with onset during the Screening Period for all subjects screened, adverse events and serious adverse events with onset after day of randomization and before day of initial device placement for the LCIG group, as well as adverse events during the transition period for LCIG subjects continuing LCIG commercial treatment will also be summarized.

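### SAP 10.2 closes the OMT adverse-event window at tube placement only for extension entrants, so events after an early switch to commercial LCIG would count against OMT

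*SAP*

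**What the plan says.** SAP 10.2 gives two rules for the OMT arm, both for the 26-week randomized period.

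- OMT subjects who stay out of the extension: "any adverse event that begins or worsens in severity the day after randomization and within 30 days following the last visit". Protocol 8.1.4.2 has the same rule for the whole arm: "For OMT group: any adverse event that begins or worsens in severity the day after randomization and within 30 days following the last visit".
- OMT subjects who enter the extension: the window closes at "30 days following the last visit during 26-week randomized treatment period or before the insertion of NJ/PEG-J (whichever is earlier").

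SAP 4.2 offers the extension only in the United States and South Korea. OMT subjects in every other country, and any in those two who decline, fall under the first rule.

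Protocol 5.1.3 says that OMT completers "are eligible to transition to commercial LCIG after end of study procedures if judged appropriate by their personal physician", and adds: "This transition is not study related". It sets no waiting period. Inclusion criterion 6 in Protocol 5.2.1 reads: "Subject is eligible to transfer to commercial treatment of Duodopa after completing the study based on local country requirements". Protocol 6.1.4 keeps collecting all adverse events, solicited or spontaneous, for 30 days past the final OMT dose or visit.

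**The concern.** An OMT subject outside the extension can finish Week 26, receive a PEG-J and start commercial LCIG inside the 30-day tail. A stoma infection, device complication or levodopa-related event in that time meets the OMT definition as written. It then enters the OMT column of the overview (SAP 10.2.1), the system-organ-class and preferred-term tables with their Fisher's exact tests (SAP 10.2.2), and the special-interest summaries (SAP 10.2.3).

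The error has one direction. It adds events typical of the LCIG system to the control arm, and so understates the excess on LCIG. Gastrointestinal and procedure-related events, the first special-interest category in Protocol 6.1.1.3, are the most exposed, because an OMT subject without a tube should have almost no device events.

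**Working it through.** No figure in the plan depends on this rule, so there is nothing to reproduce. The check sets the provisions side by side and then illustrates the size.

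**Step 1. The provisions**

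| Question | OMT, not in extension | OMT, in extension |
|---|---|---|
| Window opens | Day after randomization | Day after randomization |
| Window closes | Last visit + 30 days | Earlier of last visit + 30 days and NJ/PEG-J insertion |
| Can LCIG start inside the 30 days? | Yes, commercially (Protocol 5.1.3) | Yes, in the study |
| Where do events after the switch go? | OMT events of the randomized period | Separate extension-period definition |

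**Step 2. Does another provision close the gap?**

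- Protocol 5.1.3 says that formal data collection ends on transfer to commercial LCIG, but under the heading for LCIG-arm subjects. The OMT paragraph says only that the transition lies outside the study, which does not switch off the 30-day collection in Protocol 6.1.4.
- The Off epoch in SAP 6.2 covers OMT time after the last visit, but the event definition in SAP 10.2 does not use epochs.
- SAP Table 6 stops at Day 182. It only assigns events to study weeks and does not limit the overall, preferred-term or special-interest counts.
- The transition-period summary in SAP 10.2.1 covers LCIG-arm subjects only.

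Nothing in the readable text supplies the missing cut. Protocol 6.1.5 and the adverse-event collection figure could not be read.

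**Step 3. Share of the window exposed**

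Nominal OMT window = 182 + 30 = 212 days. The exposed tail is 30/212 = 14.2%.

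**Step 4. Illustration of size**

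Inputs:
- 44 subjects per arm (SAP 4.3).
- Device-insertion complication rate r = 33.3% (pooled open-label set, Protocol 3.2) or 56.8% (pivotal study, Protocol 3.0).
- k = number of OMT subjects outside the extension who receive a tube within 30 days of the last visit. The documents do not give k; it is assumed, from 0 to 22.

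Expected misattributed OMT subjects = k × r. The Fisher test uses rounded counts, with 15/44 LCIG subjects affected at 33.3% and 25/44 at 56.8%.

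| k (assumed) | k × 0.333 | Difference, P | k × 0.568 | Difference, P |
|---|---|---|---|---|
| 0 | 0 | 34.1 points, <0.0001 | 0 | 56.8 points, <0.0001 |
| 4 | 1.3 | 31.8 points, 0.0002 | 2.3 | 52.3 points, <0.0001 |
| 9 | 3.0 | 27.3 points, 0.003 | 5.1 | 45.5 points, <0.0001 |
| 13 | 4.3 | 25.0 points, 0.008 | 7.4 | 40.9 points, 0.0001 |
| 22 | 7.3 | 18.2 points, 0.084 | 12.5 | 29.5 points, 0.009 |

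With the cut applied to all OMT subjects, the misattributed count is 0 for any k.

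The table is not a forecast. The 33.3% comes from a pooled set with a mean of 854 days of treatment, and the 56.8% from a pivotal study whose efficacy results are given at Week 12. Follow-up after a switch would be under 30 days. The relevant base is OMT completers outside the extension, which is smaller than 44.

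**The case against.** The strongest reply is that the gap may be empty. Eligibility for commercial LCIG is not a switch, the choice rests with a personal physician, and a tube has to be arranged. United States and South Korean completers have the extension, where the cut already applies. If nobody else receives a tube within 30 days, no count changes. This stands: the documents give no number of early switchers.

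A second reply is that the cut for extension entrants may exist to stop one event being counted in two periods, since SAP 10.2 starts a separate extension window at tube placement. Subjects outside the extension have no second window, so the different wording does not prove an oversight. That is plausible, but whatever the reason for the cut, its absence still assigns events that follow a tube to OMT.

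A third reply is that the device-event contrast stays clear for any moderate k. In the table, significance is lost only at k = 22 with the lower rate, which is half the arm. These are also safety comparisons, not the primary analysis. This stands too, and limits the importance of the point.

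A reader might infer that the OMT safety rates will in fact be contaminated, or that the table estimates by how much. The documents support neither. They show a rule that would misassign such events if they occur; k is assumed and the rates are not 30-day rates.

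**Conclusion.** The concern holds as a conditional one. SAP 10.2 ends OMT attribution at tube placement for one subset and not for the other, and the other subset is allowed to start LCIG while events are still being collected. Any tube or LCIG event in such a switcher within 30 days of the last visit would be an OMT event by definition, biasing the comparison toward no difference.

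The size is unknown and may be zero. The conclusion rests on reading Protocol 6.1.4 as applying to OMT subjects after a commercial switch, and on the unreadable Protocol 6.1.5 and collection figure containing no contrary rule. The correction is worth making because the direction is unfavourable for detecting harm and the change is small.

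**What to change.** In SAP 10.2, use one rule for every OMT subject: the randomized-period window ends at the earlier of 30 days after the last visit and the date of any NJ/PEG-J placement or first LCIG dose, whether study or commercial. Align Protocol 8.1.4.2 with it.

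Add a separate summary or listing of adverse events and serious adverse events that start after the switch in OMT subjects outside the extension. Without it, the cut would drop those events from every table, because the extension and transition summaries do not cover these subjects.

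For the switch date, no new visit is needed. OMT subjects have no Visit 9 (Protocol synopsis), so the date should come from the existing 30-day adverse-event collection (Protocol 6.1.4) and the concomitant-medication record, which runs through post-study follow-up (Protocol 5.2.3.2). That record can show the start of commercial LCIG; the tube date may need its own field.

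The cost is a change of wording, one extra date to capture and one extra listing.

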5.2.3.2 Concomitant Therapy

All changes to concomitant medications must be carefully documented on the Concomitant Medication eCRF form.

Allowable Medications

Anti-Parkinsonian Medications

The following classes of anti-Parkinsonian medications will be allowed during the study:

1. Levodopa formulations
 - For the OMT group, all levodopa formulations are allowed
 - For the LCIG group:
 - levodopa formulations can only be used at nighttime (the 8 hours when the pump is not in use) or as rescue medication

- long-acting levodopa formulations can only be used at nighttime (at least 4 hours prior the next day's morning dose)
 - short-acting levodopa formulations with the exception of formulations containing entacapone can only be used at nighttime (at least 2 hours prior to the next day's morning dose) or as rescue medication
2. Dopamine agonists (not including apomorphine continuous infusion or PRN injection)
 3. MAO-B inhibitors
 4. Anti-cholinergics
 5. Amantadine

General Requirements

Screening to Visit 3: All anti-Parkinson's disease medications must be stable* for at least 30 days prior to V3 baseline assessments (NMSS and PDSS-2).

* A stable regimen is defined as no changes to the frequency of administration, dose of administration or total daily dose.

Randomization to End of Treatment Period:

- **OMT Group:** all anti-PD medications should remain stable from randomization to the Week 26 visit and study assessments. Changes to the OMT arm can be made "if medically justified."
- **LCIG Group:** all anti-PD medications except levodopa formulations must be tapered off after randomization and prior to LCIG initiation via NJ or PEG-J (in those going directly to PEG-J). Time of inverse titration should be done following the prescribing information and the Investigator's discretion, but should not exceed 14 days after randomization. For those randomized to LCIG, all allowable anti-PD medications listed above can be restarted 28 days after LCIG initiation if medically necessary for the treatment of Parkinsonian symptoms.

All medication taken by the subject during the study (from signing the Informed Consent form through post-study follow-up) is to be recorded on the Concomitant Medication eCRF, except for study drug for subjects randomized to LCIG. All changes to concomitant medications, this includes all medications taken by subjects randomized to OMT, must be carefully documented on the Concomitant Medication eCRF form.

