A Neurological Examination focusing on symptoms and signs of polyneuropathy (light touch and pinprick sensation, vibratory sensation), deep tendon reflexes, and strength assessments will be performed at the times indicated in [Table 3](#). The Neurological Examination should be bilateral and be done during the subject's "On" time.

Any abnormalities or symptoms identified at Visits 1, 2 and 3 will not be recorded as adverse events but will be recorded in Medical History eCRF. Any new abnormalities or symptoms or symptoms that change in severity or frequency following randomization for the OMT group and the first dose of IP for the LCIG group will be recorded as adverse events.

The Neurological Examination will assess:

- Cranial nerves – assessment of cranial nerves II – XII
- Motor system – assessment of tone, strength and abnormal movements
- Sensory system – including light touch, pinprick, joint position and vibratory sense
- Reflexes – assessment of deep tendon reflexes and plantar responses (Babinski sign)
- Coordination – assessment of upper and lower extremities
- Gait – assessment of base and tandem gait

The Neurological Examination performed at Visit 1, will serve as baseline for clinical assessment.

Dermatological Assessment

A comprehensive assessment by an experienced dermatologist for the presence of any suspicious skin lesions and subsequent evaluation for melanoma will be performed prior to V2 and at Week 26/Premature Discontinuation. If a suspicious lesion is present, a biopsy should be obtained for proper diagnosis and confirmation that lesion does not meet exclusion criteria.

Positive screens will be exclusionary.

GI Examination

On or prior to V2, the Investigator and GI/surgeon will thoroughly evaluate the subject's risk of undergoing PEG-J procedure.

NJ and/or PEG-J Placement (LCIG Group Only)

For subjects randomized to LCIG, a temporary NJ tube may be used to optimize the dose of LCIG before treatment with a PEG-J is started. The NJ test phase should not last longer than 7 days. Following the NJ test phase, a PEG-J will be performed by a gastroenterologist proceduralist, or surgeon. Total time to titration via NJ and PEG-J should not exceed 14 days. Alternatively, subjects may proceed directly to placement of

PEG-J if deemed appropriate by investigator. Total time to titration via the NJ and PEG-J should not exceed 14 days. The number of days to titrate will vary for each subject.

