6.1.1 Definitions

6.1.1.1 Adverse Event

An adverse event (AE) is defined as any untoward medical occurrence in a patient or clinical investigation subject administered a pharmaceutical product and which does not necessarily have a causal relationship with this treatment. An adverse event can therefore be any unfavorable and unintended sign (including an abnormal laboratory finding), symptom, or disease temporally associated with the use of a medicinal (investigational) product, whether or not the event is considered causally related to the use of the product.

Such an event can result from use of the drug as stipulated in the protocol or labeling, as well as from accidental or intentional overdose, drug abuse, or drug withdrawal. Any worsening of a pre-existing condition or illness is considered an adverse event.

Worsening in severity of a reported adverse event should be reported as a new adverse event. Laboratory abnormalities and changes in vital signs are considered to be adverse events only if they result in discontinuation from the study, necessitate therapeutic medical intervention, and/or if the Investigator considers them to be adverse events.

An elective surgery/procedure scheduled to occur during a study will not be considered an adverse event if the surgery/procedure is being performed for a pre-existing condition and the surgery/procedure has been pre planned prior to study entry. However, if the pre-existing condition deteriorates unexpectedly during the study (e.g., surgery performed earlier than planned), then the deterioration of the condition for which the elective surgery/procedure is being done will be considered an adverse event. Also, fluctuating PD symptoms during titration should not be considered an adverse event.

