6.1.4 Adverse Event Collection Period

Protocol-related nonserious adverse events that occur after signing the informed consent, prior to the start of study drug administration, will be collected. All adverse events reported from the time of randomization until 30 days following last OMT dose, last study visit, discontinuation of study drug administration, removal of the PEG-J tube or Last LCIG Commercial Transition Visit have elapsed will be collected, whether solicited or spontaneously reported by the subject. In addition, serious adverse events and protocol related non serious adverse events will be collected from the time the subject signed the study-specific informed consent.

Adverse event information will be collected as shown in [Figure 3](#).

Figure 3. Adverse Event Collection

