8.0 Statistical Methods and Determination of Sample Size

8.1 Statistical and Analytical Plans

8.1.1 Analysis Datasets

Intent-to-Treat Dataset

Unless specified otherwise, the efficacy analyses will be performed on the intent-to-treat dataset which will include all subjects who are randomized to the optimized medical treatment, and all subjects who are randomized to LCIG and received at least one dose of study drug. For assessments of efficacy, the treatment period will begin the day after randomization for subjects randomized to optimized medical treatment, and the day of first LCIG infusion following PEG-J placement for subjects randomized to LCIG

treatment. The treatment period will end on the day of the final visit for subjects randomized to OMT, and on the last day of LCIG study drug infusion for subjects randomized to LCIG treatment.

The last assessment prior to randomization will be considered baseline and the last assessment that is no more than 2 days after the end of the treatment period will be considered the final evaluation.

Safety Dataset

The safety analyses will be performed on the safety dataset which will include all subjects who are randomized to the optimized medical treatment, and all subjects who are randomized to LCIG and have study device (NJ and/or PEG-J) placement. For assessments of safety, the treatment period will begin the day after randomization for subjects randomized to optimized medical treatment, and the day of NJ placement (or PEG-J placement if no NJ) for subjects randomized to LCIG. The treatment period will end on the day of the final visit for subjects randomized to optimized treatment, and on the last day of LCIG infusion or device removal (whichever is later) in the study for subjects randomized to LCIG. The last assessment prior to randomization will be considered baseline and the last assessment that is no more than 2 days after the end of the treatment period will be considered the final evaluation.

8.1.2 Demographic, Other Baseline Characteristics, Subject Disposition, and Concomitant Medication

Demographic and Other Baseline Characteristics

All demographic variables will be summarized for the safety dataset unless otherwise specified.

For continuous demographic variables, including age, weight, height and body mass index (BMI), descriptive statistics (number of subjects with non-missing data, mean, standard deviation, median, minimum, and maximum) will be provided for each treatment group,

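### The between-arm adverse event comparison starts the day after randomization for OMT but at tube placement for LCIG, so events that begin during the LCIG-only drug taper are reported but never compared with OMT

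*SAP*

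**What the plan says.** **Start of the compared window.** For OMT subjects who do not enter the extension, SAP 10.2 counts "any adverse event that begins or worsens in severity the day after randomization and within 30 days following the last visit". For those who do, the start is the same. For LCIG, "this includes all adverse events with onset on or after the date of the initial tube placement procedure". Protocol 8.1.4.2 defines the LCIG start in the same way, and Protocol 8.1.1 starts the LCIG safety treatment period on "the day of NJ placement (or PEG-J placement if no NJ) for subjects randomized to LCIG". SAP 6.2 puts all LCIG time before device placement in the Pre epoch, whereas for OMT that epoch ends on the day of randomization.

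**What happens in between.** Protocol 5.2.3.2 states that in the LCIG group "all anti-PD medications except levodopa formulations must be tapered off after randomization and prior to LCIG initiation". Sections 5.1.2.2 and 5.2.3.2 limit the taper to 14 days after randomization. OMT subjects stay on their regimen.

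**Who is compared, and how.** SAP 5.0 includes every subject randomized to OMT in the Safety Dataset, but only those LCIG subjects who had a device placed. SAP 10.1 makes that the default set for safety analyses. SAP 10.2.2 applies Fisher's exact test to the percentages with any TEAE, any serious TEAE and any TEAE leading to discontinuation.

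**What is collected and reported.** Protocol 6.1.4 covers "All adverse events reported from the time of randomization until 30 days following last OMT dose" and other end points. Protocol 8.1.4.2 and SAP 10.2.1 both plan a summary of LCIG adverse events and serious adverse events that begin after randomization and before device placement. No OMT comparator is planned for it.

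**Neurological findings.** Protocol 5.3.1.1 says that new or changed findings "following randomization for the OMT group and the first dose of IP for the LCIG group will be recorded as adverse events".

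**The concern.** A secondary objective is safety and tolerability of LCIG relative to OMT. Assignment to LCIG is what triggers the taper, and the adverse event definition in Protocol 6.1.1.1 covers events that result from drug withdrawal. Protocol 5.6.1 also argues for the open-label design partly on the ground that most patients take other anti-PD drugs and that OMT subjects could not safely be kept on levodopa alone for 28 days. The start of that same phase in the LCIG arm lies outside the randomized comparison of adverse events.

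At stake is whether the headline table compares the two assigned strategies from the point at which they diverge, or compares OMT from randomization with LCIG from a later landmark. Subjects who drop out before the landmark are lost from the LCIG side only.

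**Working it through.** The plan gives no figure to reproduce here: no taper event rate, no safety power, and no expected time from randomization to placement. The check therefore sets the definitions side by side, followed by arithmetic on the gap.

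**1. Uncounted time after randomization**

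| | OMT | LCIG |
|---|---|---|
| First counted day | day after randomization | day of first tube placement |
| Uncounted days | 0 | up to 14 at the taper limit |
| Subjects in the set | all randomized | only those with a device placed |

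The 14 days is a limit on the taper. The documents state no cap on the time from randomization to placement, so the gap may be longer. As a share of a 182-day treatment period:
- 14 days: 14/182 = 7.7%
- 21 days (assumed): 21/182 = 11.5%
- 28 days (assumed): 28/182 = 15.4%

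**2. Follow-up length**

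Protocol 5.3.1 counts visits from Study Day 1, which is placement in LCIG and the day after randomization in OMT. Each arm therefore has about 26 × 7 = 182 planned days. The windows differ in where they start, not in length. Running both arms from randomization to their own Week 26 visit would give LCIG up to 14 + 182 = 196 days against 182 for OMT, which would tilt crude incidence against LCIG. A fair common-start comparison needs an equal fixed end or exposure adjustment.

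**3. What Table 1 can and cannot tell us**

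Protocol Table 1 lists Parkinson's disease as a TEAE in 14.3% of 412 subjects, over a mean of 854 days on LCIG. At a constant hazard, the share expected in 14 days is 1 − (1 − 0.143)^(14/854) = 0.25%, or 44 × 0.0025 ≈ 0.1 subject. That rate was measured on LCIG, not during a pre-LCIG taper, so it neither supports nor excludes a material rate in the gap.

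**4. How the table could change (all counts assumed, 44 per arm, two-sided Fisher test)**

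| Planned table, LCIG vs OMT | LCIG taper-only subjects added | Common start | P value |
|---|---|---|---|
| 0 vs 0 | 4 | 4 vs 0 | 2 × C(44,4)/C(88,4) = 0.116 |
| 0 vs 0 | 6 | 6 vs 0 | 2 × C(44,6)/C(88,6) = 0.026 |
| 4 vs 4 | 6 | 10 vs 4 | 0.143 |
| 4 vs 4 | 9 | 13 vs 4 | 0.029 |

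Six of 44 is 13.6%. About that many subjects would need to have their only event of a given kind in the gap before a table showing no events in either arm reached nominal significance. These rows show sensitivity and are not a forecast.

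**5. Neurological findings**

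Protocol 6.1.4 collects all adverse events from randomization in both arms. The Neurological Examination text in 5.3.1.1 starts recording at randomization for OMT but at first dose for LCIG. First dose can fall after placement, since 5.1.2.2 allows around 48 hours for a passively placed NJ tube. The two sections do not agree. The practical effect is probably small: the schedule, as far as the extracted table can be read, shows no neurological examination between V3 and Week 2, so a change first seen at Week 2 may still be recorded.

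**The case against.** The strongest reply is that nothing is hidden. The plan collects events from randomization, pre-specifies a summary of exactly this interval, counts LCIG subjects with no tube placed in the disposition table (SAP 7.1), and lists deaths for everyone screened (SAP 10.2.5). Protocol 6.1.3 treats LCIG as a system of drug, devices and placement procedure, so a window that opens at the first of these is a coherent on-treatment definition. Levodopa continues through the taper, and some subjects may have nothing else to withdraw. All of this stands, and it is why the existing TEAE tables should stay. It does not answer the objective as worded, which is relative to OMT: the separate summary has no comparator and, by default, omits those who never reached placement.

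A reader might go further in four directions that the documents do not support.
- **That LCIG follow-up is shorter.** It is not; the full 26 weeks from placement are counted. Withdrawal effects that begin after placement also count as LCIG events.
- **That LCIG harm is shown to be understated by some number of subjects.** Any taper rate is an assumption, and the 14.3% in Table 1 covers a mean of 854 days on treatment.
- **That polyneuropathy is being missed.** The protocol presents it as an event of special interest related to LCIG, which has not been given during the taper.
- **That the sentence "Also, fluctuating PD symptoms during titration should not be considered an adverse event" is part of the same problem.** Titration follows tube placement, so that rule has no bearing on when the window opens and is a separate matter.

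**Conclusion.** The asymmetry is in the text and holds for the between-arm adverse event comparison. OMT is counted from the day after randomization on all randomized subjects. LCIG is counted from tube placement, on those who received a tube. Events that begin during the mandated LCIG-only taper are reported separately but not compared, and subjects who leave during it are by default in neither table.

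The uncounted interval is up to 14 days at the stated taper limit, possibly longer because placement has no stated deadline. Its effect on event rates cannot be estimated from the documents. The direction would be unfavourable to LCIG only if the taper produces events at a higher rate than OMT over the same days, which is plausible from Protocol 5.6.1 but not shown. This is a gap in what is compared, not in what is collected. It can be closed from data already specified, apart from the conflict over neurological findings.

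**What to change.** 1. **SAP 10.2.1 and 10.2.2.** Add a supplementary comparison of adverse events, serious adverse events and adverse events leading to discontinuation on the All Randomized Dataset, which SAP 5.0 already defines. Start both arms the day after randomization and end both at the same fixed number of days after randomization, for example 182, or use exposure-adjusted rates. Do not end each arm at its own Week 26 visit, for the reason in step 2 of the working. Keep the current TEAE tables for drug and device attribution.
2. **SAP 10.2.1.** State that the summary of events between randomization and device placement covers all subjects randomized to LCIG, including those never given a tube.
3. **Protocol 5.3.1.1 and 6.1.4.** Reconcile the two sections so that recording of new or changed neurological findings starts at the same point in both arms.

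The cost is a few extra tables, one clarifying SAP line and one protocol sentence. No new data collection is needed for items 1 and 2. The downside is that the added LCIG rates will include events before the first LCIG dose, so they need a label saying that they describe the assigned strategy, not the drug or device alone. With a 182-day limit, the last days of LCIG treatment fall outside the supplementary table, but they remain in the TEAE tables.
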